12.0 RETENTION OF RECORDS

12.1 A Case Report Form will be provided by the Clinical Trials Office and submitted once completed. Periodic monitoring of this CRF will be done to ascertain compliance with source documentation requirements.

ULEU-13049 34 Version date: 09Aug2017

U.S. FDA regulations (21 CFR 312.62]) require that records and documents pertaining to the conduct of this study including CRFs, consent forms, laboratory test results, and medication inventory records, must be retained by the Principal Investigator as required by the University of Rochester.

13.0 PATIENT CONSENT AND PEER JUDGEMENT

All institutional, NCI, FDA, State, and Federal regulations concerning informed consent and peer judgment will be fulfilled.

14.0 CHANGES IN PROTOCOL

Any change or addition to this protocol requires a written protocol amendment that must be approved by the investigator before implementation. Amendments significantly affecting the safety of subjects, the scope of the investigation or the scientific quality of the study, require additional approval by the RSRB of the University of Rochester.

Amendments affecting only administrative aspects of the study do not require formal protocol amendments or IRB approval but the IRB of each center must be kept informed of such administrative changes

15.0 REASONS FOR WITHDRAWAL

A patient may withdraw from the study at any time for any reason, and patients are under no obligation to explain reason for withdrawal although this will be queried. Any patient may be discontinued from study in the event of progressive disease, unacceptable drug toxicity, patient refusal to continue on study, or if in the physician's judgment discontinuation is in the best interest of the patient.


ULEU-13049 37 Version date: 09Aug2017

Performance Status Criteria

ECC	OG Performance Status Scale	Karnofsky Performance Scale							
Grade	Descriptions	Percent	Description						
0	Normal activity. Fully active, able to carry on all pre-disease	100	Normal, no complaints, no evidence of disease.						
U	performance without restriction.	90	Able to carry on normal activity; minor signs or symptoms of disease.						
1	Symptoms, but ambulatory. Restricted in physically strenuous activity, but ambulatory and able	80	Normal activity with effort; some signs or symptoms of disease.						
	to carry out work of a light or sedentary nature (e.g., light housework, office work).	70	Cares for self, unable to carry on normal activity or to do active work.						
2	In bed <50% of the time. Ambulatory and capable of all self-care, but unable to carry out	60	Requires occasional assistance, but is able to care for most of his/her needs.						
	any work activities. Up and about more than 50% of waking hours.	50	Requires considerable assistance and frequent medical care.						
3	In bed >50% of the time. Capable of only limited self-care, confined	40	Disabled, requires special care and assistance.						
3	to bed or chair more than 50% of waking hours.	30	Severely disabled, hospitalization indicated. Death not imminent.						
4	100% bedridden. Completely disabled. Cannot carry on any	20	Very sick, hospitalization indicated. Death not imminent.						
4	self-care. Totally confined to bed or chair.	10	Moribund, fatal processes progressing rapidly.						
5	Dead.	0	Dead.						

Cockcroft-Gault Equation: (140-age)*wt/(Cr*72)

Common Terminology Criteria for Adverse Events (CTCAE), version 4.0 (http://ctep.cancer.gov)

Publish Date: June 14, 2010

Pdf: http://evs.nci.nih.gov/ftp1/CTCAE/CTCAE 4.03 2010-06-14 QuickReference 8.5x11.pdf

ULEU-13049 41 Version date: 09Aug2017

Declaration of Helsinki

World Medical Association Declaration of Helsinki:

Ethical Principles for Medical Research Involving Human Subjects
Adopted by the 18th WMA General Assembly Helsinki, Finland, June 1964 and amended by the
29th WMA General Assembly, Tokyo, Japan, October 1975 35th WMA General Assembly,
Venice, Italy, October 1983 41st WMA General Assembly, Hong Kong, September 1989 48th
WMA General Assembly, Somerset West, Republic of South Africa, October 1996 and the 52nd
WMA General Assembly, Edinburgh, Scotland.

A. INTRODUCTION

- 1. The World Medical Association has developed the Declaration of Helsinki as a statement of ethical principles to provide guidance to physicians and other participants in medical research involving human subjects. Medical research involving human subjects includes research on identifiable human material or identifiable data.
- 2. It is the duty of the physician to promote and safeguard the health of the people. The physician's knowledge and conscience are dedicated to the fulfillment of this duty.
- 3. The Declaration of Geneva of the World Medical Association binds the physician with the words, "The health of my patient will be my first consideration," and the International Code of Medical Ethics declares that, "A physician shall act only in the patient's interest when providing medical care which might have the effect of weakening the physical and mental condition of the patient."
- 4. Medical progress is based on research which ultimately must rest in part on experimentation involving human subjects.
- 5. In medical research on human subjects, considerations related to the well-being of the human subject should take precedence over the interests of science and society.
- 6. The primary purpose of medical research involving human subjects is to improve prophylactic, diagnostic and therapeutic procedures and the understanding of the etiology and pathogenesis of disease. Even the best proven prophylactic, diagnostic, and therapeutic methods must continuously be challenged through research for their effectiveness, efficiency, accessibility and quality.
- 7. In current medical practice and in medical research, most prophylactic, diagnostic and therapeutic procedures involve risks and burdens.
- 8. Medical research is subject to ethical standards that promote respect for all human beings and protect their health and rights. Some research populations are vulnerable and need special protection. The particular needs of the economically and medically disadvantaged must be recognized. Special attention is also required for those who cannot give or refuse consent for themselves, for those who may be subject to giving consent under duress, for those who will not benefit personally from the research and for those for whom the research is combined with care.

ULEU-13049 42 *Version date: 09Aug2017*

9. Research Investigators should be aware of the ethical, legal and regulatory requirements for research on human subjects in their own countries as well as applicable international requirements. No national ethical, legal or regulatory requirement should be allowed to reduce or eliminate any of the protections for human subjects set forth in this Declaration.

B. BASIC PRINCIPLES FOR ALL MEDICAL RESEARCH

- 1. It is the duty of the physician in medical research to protect the life, health, privacy, and dignity of the human subject.
- 2. Medical research involving human subjects must conform to generally accepted scientific principles, be based on a thorough knowledge of the scientific literature, other relevant sources of information, and on adequate laboratory and, where appropriate, animal experimentation.
- 3. Appropriate caution must be exercised in the conduct of research which may affect the environment, and the welfare of animals used for research must be respected.
- 4. The design and performance of each experimental procedure involving human subjects should be clearly formulated in an experimental protocol. This protocol should be submitted for consideration, comment, guidance, and where appropriate, approval to a specially appointed ethical review committee, which must be independent of the investigator, the sponsor or any other kind of undue influence. This independent committee should be in conformity with the laws and regulations of the country in which the research experiment is performed. The committee has the right to monitor ongoing trials. The researcher has the obligation to provide monitoring information to the committee, especially any serious adverse events. The researcher should also submit to the committee, for review, information regarding funding, sponsors, institutional affiliations, other potential conflicts of interest and incentives for subjects.
- 5. The research protocol should always contain a statement of the ethical considerations involved and should indicate that there is compliance with the principles enunciated in this Declaration.
- 6. Medical research involving human subjects should be conducted only by scientifically qualified persons and under the supervision of a clinically competent medical person. The responsibility for the human subject must always rest with a medically qualified person and never rest on the subject of the research, even though the subject has given consent.
- 7. Every medical research project involving human subjects should be preceded by careful assessment of predictable risks and burdens in comparison with foreseeable benefits to the subject or to others. This does not preclude the participation of healthy volunteers in medical research. The design of all studies should be publicly available.
- 8. Physicians should abstain from engaging in research projects involving human subjects unless they are confident that the risks involved have been adequately assessed and can be satisfactorily managed. Physicians should cease any investigation if the risks are found to outweigh the potential benefits or if there is conclusive proof of positive and beneficial results.
- 9. Medical research involving human subjects should only be conducted if the importance of the objective outweighs the inherent risks and burdens to the subject. This is especially important when the human subjects are healthy volunteers.

ULEU-13049 43 *Version date: 09Aug2017*

- 10. Medical research is only justified if there is a reasonable likelihood that the populations in which the research is carried out stand to benefit from the results of the research.
- 11. The subjects must be volunteers and informed participants in the research project.
- 12. The right of research subjects to safeguard their integrity must always be respected. Every precaution should be taken to respect the privacy of the subject, the confidentiality of the patient's information and to minimize the impact of the study on the subject's physical and mental integrity and on the personality of the subject.
- 13. In any research on human beings, each potential subject must be adequately informed of the aims, methods, sources of funding, any possible conflicts of interest, institutional affiliations of the researcher, the anticipated benefits and potential risks of the study and the discomfort it may entail. The subject should be informed of the right to abstain from participation in the study or to withdraw consent to participate at any time without reprisal. After ensuring that the subject has understood the information, the physician should then obtain the subject's freely-given informed consent, preferably in writing. If the consent cannot be obtained in writing, the non-written consent must be formally documented and witnessed.
- 14. When obtaining informed consent for the research project the physician should be particularly cautious if the subject is in a dependent relationship with the physician or may consent under duress. In that case the informed consent should be obtained by a well-informed physician who is not engaged in the investigation and who is completely independent of this relationship.
- 15. For a research subject who is legally incompetent, physically or mentally incapable of giving consent or is a legally incompetent minor, the investigator must obtain informed consent from the legally authorized representative in accordance with applicable law. These groups should not be included in research unless the research is necessary to promote the health of the population represented and this research cannot instead be performed on legally competent persons.
- 16. When a subject deemed legally incompetent, such as a minor child, is able to give assent to decisions about participation in research, the investigator must obtain that assent in addition to the consent of the legally authorized representative.
- 17. Research on individuals from whom it is not possible to obtain consent, including proxy or advance consent, should be done only if the physical/mental condition that prevents obtaining informed consent is a necessary characteristic of the research population. The specific reasons for involving research subjects with a condition that renders them unable to give informed consent should be stated in the experimental protocol for consideration and approval of the review committee. The protocol should state that consent to remain in the research should be obtained as soon as possible from the individual or a legally authorized surrogate.
- 18. Both authors and publishers have ethical obligations. In publication of the results of research, the investigators are obliged to preserve the accuracy of the results. Negative as well as positive results should be published or otherwise publicly available. Sources of funding, institutional affiliations and any possible conflicts of interest should be declared in the publication. Reports of experimentation not in accordance with the principles laid down in this Declaration should not be accepted for publication.

ULEU-13049 44 Version date: 09Aug2017

C. ADDITIONAL PRINCIPLES FOR MEDICAL RESEARCH COMBINED WITH MEDICAL CARE

- 1. The physician may combine medical research with medical care, only to the extent that the research is justified by its potential prophylactic, diagnostic or therapeutic value. When medical research is combined with medical care, additional standards apply to protect the patients who are research subjects.
- 2. The benefits, risks, burdens and effectiveness of a new method should be tested against those of the best current prophylactic, diagnostic, and therapeutic methods. This does not exclude the use of placebo, or no treatment, in studies where no proven prophylactic, diagnostic or therapeutic method exists.
- 3. At the conclusion of the study, every patient entered into the study should be assured of access to the best proven prophylactic, diagnostic and therapeutic methods identified by the study.
- 4. The physician should fully inform the patient which aspects of the care are related to the research. The refusal of a patient to participate in a study must never interfere with the patient-physician relationship.
- 5. In the treatment of a patient, where proven prophylactic, diagnostic and therapeutic methods do not exist or have been ineffective, the physician, with informed consent from the patient, must be free to use unproven or new prophylactic, diagnostic and therapeutic measures, if in the physician's judgment it offers hope of saving life, re-establishing health or alleviating suffering. Where possible, these measures should be made the object of research, designed to evaluate their safety and efficacy. In all cases, new information should be recorded and, where appropriate, published. The other relevant guidelines of this Declaration should be followed.

ULEU-13049 45 Version date: 09Aug2017

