3.1.7 ECOG performance status <3 (Appendix 1)

3.2 Exclusion Criteria

- 3.2.1 Abnormal renal function as evidenced by a calculated creatinine clearance ≤ 30 ml/min (Cockcroft-Gault formula (Appendix 2)
- 32.2 Abnormal liver function: Bilirubin >2.0 mg/dl, transaminase(s) more than
- 2.5x the upper limits of normal
- 3.2.3 Active systemic infection not responding to antibiotics
- 3.2.4 Known diagnosis of human immunodeficiency virus infection (HIV)
- 3.2.5 Patients who are post-allogeneic transplantation should not have active GVHD greater than grade 1 of skin at time of enrollment. They may have had DLI but not within 4 weeks of beginning the study.
- 3.2.6 Pregnant or breast feeding female subjects
- 3.2.7 Known or suspected CNS leukemia involvement; past involvement is not an exclusion.

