3.3 Inclusion of Women and Minorities

Both men and women and members of all ethnic groups are eligible for this trial.

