5.3.2 CLINICAL PHARMACOLOGY

Mechanism of Action

• Ribavirin is an antiviral drug

Pharmacokinetics

- Multiple dose ribavirin pharmacokinetic data are available for HCV patients who received ribavirin in combination with peginterferon alfa-2a. Following administration of 1200 mg/day with food for 12 weeks mean±SD (n=39; body weight greater than 75 kg) AUC0-12hr was 25,361±7110 ng·hr/mL and Cmax was 2748±818 ng/mL. The average time to reach Cmax was 2 hours.
- The terminal half-life of ribavirin following administration of a single oral dose of is about 120 to 170 hours. The total apparent clearance following administration of a single oral dose of is about 26 L/h. There is extensive accumulation of

ULEU-13049 25 Version date: 09Aug2017

ribavirin after multiple dosing (twice daily) such that the Cmax at steady state was four-fold higher than that of a single dose.

Effect of Food on Absorption of Ribavirin

- Bioavailability of a single oral dose of ribavirin was increased by coadministration with a high-fat meal.
- Elimination and Metabolism
- The contribution of renal and hepatic pathways to ribavirin elimination after administration of is not known. In vitro studies indicate that ribavirin is not a substrate of CYP450 enzymes.
- Renal Impairment
- A clinical trial evaluated 50 subjects with either moderate (creatinine clearance 30 to 50 mL/min) or severe (creatinine clearance less than 30 mL/min) renal impairment or end stage renal disease (ESRD) requiring chronic hemodialysis (HD). The apparent clearance of ribavirin was reduced in subjects with creatinine clearance less than or equal to 50 mL/min, including subjects with ESRD on HD, exhibiting approximately 30% of the value found in subjects with normal renal function. Pharmacokinetic modeling and simulation indicates that a dose of 200 mg daily in patients with severe renal impairment and a dose of 200 mg daily alternating with 400 mg the following day in patients with moderate renal impairment will provide plasma ribavirin exposures similar to that observed in patients with normal renal function receiving the standard 1000/1200 mg daily dose. These doses have not been studied in patients.

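### Appendix 2, as extracted, prints Cockcroft-Gault with no sex term or units; read literally, exclusion 3.2.1 could admit women whose sex-adjusted clearance is just under 30 mL/min

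*Combined protocol and SAP*

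**What the plan says.** Section 3.2, item 3.2.1, sets the renal exclusion as "Abnormal renal function as evidenced by a calculated creatinine clearance ≤ 30 ml/min (Cockcroft-Gault formula (Appendix 2" (closing brackets not shown). The criterion both names an equation and points to an appendix for it, so Appendix 2 is the working definition of an eligibility limit.

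The equation stands after the reference list, between the performance status table and the toxicity criteria, where the outline places Appendix 2. It reads "Cockcroft-Gault Equation: (140-age)*wt/(Cr*72", followed by a closing bracket. It is a single expression. It has no multiplier for women and no units for age, weight or creatinine.

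Section 3.3 states that "Both men and women and members of all ethnic groups are eligible for this trial". No other section supplies a sex term or says that one applies.

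On relevance, section 5.3.2 reports that "The apparent clearance of ribavirin was reduced in subjects with creatinine clearance less than or equal to 50 mL/min", and it separates moderate from severe renal impairment at 30 mL/min. Section 4.4 makes the rapamycin and ribavirin doses fixed, non-calculated doses.

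**The concern.** The protocol names a specific equation but prints only part of its conventional form. For a man the two agree. For a woman the printed line gives a larger number than the equation with a female factor below 1, so the same limit of 30 mL/min is in effect set lower for women than for men. Item 3.2.1 states no such difference.

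Two people applying 3.2.1 in good faith could therefore decide differently on the same woman, one using the printed line and the other a calculator with a sex term built in. What is at stake is a safety-related entry criterion. Newly diagnosed patients enter only above age 65 (3.1.6), and the formula falls with age, so values near the limit are plausible. The missing units are a smaller gap, but an equation that defines eligibility should state them.

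**Working it through.** The documents report no clearance value and no count of affected women, so there is no plan figure to reproduce. The check is direct arithmetic.

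**Inputs**
- Printed equation (Appendix 2): C = (140 − age) × weight / (72 × creatinine).
- Exclusion limit (3.2.1): C ≤ 30 mL/min.
- Female factor f: not in the documents. f = 0.85 is assumed as the conventional value, with 0.80 to 0.95 shown as a range.
- Units for the example: years, kg, mg/dL (assumed, since the appendix gives none).

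**Overstatement.** The adjusted value is f × C, so the printed value exceeds it by 1/f − 1. With f = 0.85 this is 1/0.85 − 1 = 17.6%.

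**Band in which the decision changes.** The printed line admits when C > 30. The adjusted line excludes when f × C ≤ 30, that is, when C ≤ 30/f. The two disagree for 30 < C ≤ 30/f, or on the adjusted scale for 30f < value ≤ 30. With f = 0.85, 30/0.85 = 35.3 and 30 × 0.85 = 25.5.

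| f (assumed) | Overstatement | Printed value, mL/min | Adjusted value, mL/min |
|---|---|---|---|
| 0.80 | 25.0% | above 30, up to 37.5 | above 24.0, up to 30 |
| 0.85 | 17.6% | above 30, up to 35.3 | above 25.5, up to 30 |
| 0.90 | 11.1% | above 30, up to 33.3 | above 27.0, up to 30 |
| 0.95 | 5.3% | above 30, up to 31.6 | above 28.5, up to 30 |

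**Worked cases, women, f = 0.85**
- Age 75, 60 kg, creatinine 1.6: (65 × 60)/(1.6 × 72) = 33.9 as printed, which admits; 33.85 × 0.85 = 28.8 adjusted, which excludes.
- Same woman, creatinine 2.2: 24.6 printed and 20.9 adjusted. She is excluded either way.
- Age 70, 65 kg, creatinine 1.0: (70 × 65)/(1.0 × 72) = 63.2 printed and 53.7 adjusted. She is eligible either way.

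**Width of the window.** At age 75 and 60 kg the printed line excludes from creatinine (65 × 60)/(72 × 30) = 1.81 mg/dL upward, and the adjusted line from 0.85 × 1.806 = 1.53 mg/dL upward. The decision differs only from about 1.53 to just under 1.81 mg/dL.

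**The case against.** Several objections narrow the point.

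- **The factor comes from outside the documents.** Without it the documents do not contradict themselves. This stands, so 0.85 is labelled an assumption with a range. The direction does not depend on the exact value, because any factor below 1 makes the printed line the more permissive one for women. The absence of units needs no outside source.
- **Text may have been lost.** In the extracted text the footers for pages 38 to 40 and the headings of Appendices 1 to 3 do not appear near the equation, so a second line could have been dropped. The surviving line reads as complete and carries no redaction or figure marker, but only the source page settles this.
- **Sites may not have used the printed line.** Because 3.2.1 names the equation, a laboratory or calculator with a sex term may have been used. The documents do not show which.
- **Few women can be affected.** Arm A has at most 24 evaluable patients and the Arm B escalation at most 6 per dose level. The number of women in so narrow a band may be zero.

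A reader might also infer that the ribavirin data in section 5.3.2 measure the harm. They do not. The figure there, apparent clearance about 30% of normal, pools everyone at or below 50 mL/min, including dialysis patients. The 30 mL/min limit already admits patients of both sexes between 30 and 50 on fixed doses, so that exposure question exists with or without the sex term. For Arm A, section 5.2 lists 2.2% urinary excretion of rapamycin, and no consequence specific to that arm is shown.

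**Conclusion.** The point holds in a limited form. As extracted, Appendix 2 is the operative formula for a renal exclusion, and it omits both a sex term and units in a trial open to women. If the intended equation carries the conventional factor of 0.85, literal use overstates women's clearance by 17.6% and reverses the decision only for adjusted values above 25.5 and up to 30 mL/min.

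Two stronger readings are tempting and are not supported. One is that women below 30 mL/min are admitted in general: under the same assumption, those at 25.5 or below are excluded by either calculation. The other is that ineligible women were in fact enrolled: the documents report no such patient and do not say how clearance was calculated in practice.

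The conclusion rests on three conditions: the source page matches the extracted line, the named equation is meant in its conventional form, and the printed line is applied as written. The Arm A sample size does not depend on it.

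**What to change.** 1. Check the source page of Appendix 2 for a line lost in extraction. If the sex term and units are there, nothing further is needed.
2. If they are absent, replace the line with the full named equation, including its female factor, and state the units (years, kg, mg/dL). The factor should be taken from the equation's source reference, since the protocol does not give it.
3. Align the eligibility checklist used at registration (section 4.1.3), so that 3.2.1, Appendix 2 and the checklist give the same answer.
4. For any registered woman with a printed value of about 30 to 36 mL/min (30 to 35.3, rounded outward), confirm which calculation was used and document it.

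The 30 mL/min limit stays as it is. The cost is one line in an appendix, a checklist edit and a short record check. The downside is small: a few women close to the limit would become ineligible.
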